Silicosis Prevalence and Related Knowledge, Attitudes and Practices Among Rural Mine Workers in Rwanda

A Study Supported by Partners in Health/Inshuti Mu Buzima Non-Communicable Disease Programs

RNEC Approval 4/11/2022

NCT05538299

Project Summary:

Silicosis is the most prevalent occupational lung disease in low- and middle-income countries (LMICs) with "tens of millions" estimated to suffer from the disease according to the World Health Organization (WHO). To date, there is little published data on silicosis in LMICs and the burden of silicosis in Rwanda has not been well-defined. Silicosis among local mine workers is a common reason for hospitalization and death at Rwinkwavu District Hospital, located in Rwanda's Kayonza District.

The objectives of this study are:

- 1. To assess the prevalence of silicosis among workers in four mines located in the Kayonza District of Rwanda
- 2. To adapt a validated screening tool testing in Dutch construction workers for Rwandan miners
- 3. To implement an occupational health education program and assess the change of before and after intervention that target towards proper use of PPE and individual risk assessment in mine workers using knowledge-attitudes-practice tool

Name	Relevant Title and Institution	Location	Research Role
[name]	Director of Social and Community Medicine, PIH	Rwanda	General project oversight, study design, results interpretation, manuscript writing and review.
[name]	Internal Medicine Doctor	Rwanda and USA	General project oversight, study design, results interpretation, manuscript writing and review.
[name] MSc	Internal Medicine Doctor	Rwanda and USA	General project oversight, study design, results interpretation, manuscript writing and review.
[name]	Director of Research and Training, PIH	Rwanda	General project oversight, study design, results interpretation, manuscript writing and review
[name]	Data analyst, PIH	Rwanda	Support study design, data management, analysis, interpretation, manuscript writing.
[name]	Internal Medicine Doctor, RDH	Rwanda	General project oversight, study design, results interpretation, manuscript writing and review.

Investigators:

[name],	Assistant Professor,	USA	Study design, data interpretation,	
MD	Medicine, UCSF		manuscript review, dissemination	
[name]	Director General, RDH	Rwanda	Study design, data interpretation, manuscript review, dissemination	
[name]	Clinical Director, RDH			

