Silicosis is deadly, but it is also preventable. In recent decades, incidence rates have declined in some countries after the institution of effective occupational health measures. Eliminating the medical and socioeconomic toll of silicosis requires primary prevention through a hierarchy of controls as shown in Fig. 2 and early detection and mitigation through screening and surveillance. Mining operations will always encounter silica dust and this hazard cannot be substituted. Therefore, the most effective and practical approach to silicosis prevention in mining operations involves engineering controls, which isolate workers from RCS. Commonly used engineering controls in mining include ventilation systems, enclosed cabs or booths with air filtration, and water spray and other wetting systems to reduce dust entrainment. Administrative controls, such as hazard education, worker hygiene and job rotation, along with personal protective equipment (PPE) such as air filtration masks supplement the protective effect of engineering controls, however they are somewhat less effective. Administrative controls and PPE also depend on the behavior of each individual worker, and are therefore less reliable. Primary prevention through dust control along with early detection of disease, health education, and strong regulatory oversight, are consistent with joint ILO/WHO Global Programme for the Elimination of Silicosis (GPES).

Figure 2 – Hierarchy of controls in occupational health

[figure not shown]

Source: United States National Institute for Occupational Safety and Health (NIOSH)

Silicosis is an insidious disease, commonly taking years to develop into clinically identifiable signs or symptoms. In the absence of regular screening and surveillance, the diagnosis of silicosis is usually not made until an extensive level of irreversible lung damage and significant physical debility have already occurred. Among workers exposed to RCS, chest radiography, commonly referred to as Chest X-ray, is among the most important clinical tools for identifying silicosis, along with spirometry, which carefully measures airflow dynamics during breathing, and symptom checklists.

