Recurrent exposure to RCS is the single most important risk factor for developing silicosis. Both disease risk and severity increase proportionally with the total cumulative amount of inhaled RCS over person's lifetime. Other factors associated with silicosis are well-documented, including tobacco smoking, older age, limited education, migrant status, and delays in medical care. An array of additional factors, from individual education and income levels to political economy in poor communities, shape how silicosis arises and makes an impact both in the individual and collective, fractal life of each person living with silicosis. We have developed a biosocial conceptual framework for understanding silicosis, specifically as it manifests in Rwanda.

Figure 3 – Biosocial conceptual framework for silicosis in Rwanda

Based on the clinical experience of the authors and their network, silicosis morbidity and mortality have been consistently encountered among Rwandans with dust and mining exposure, however Rwanda currently lacks an existing body of data on current silicosis prevalence and a surveillance system for ongoing monitoring and interventions. According to the WHO, disease surveillance programs should include periodic identification and collection of health information, evaluation and interpretation of the information, and reporting and interventions for the purpose of prevention. The goal of surveillance is to monitor the trends in disease incidence over time across a particular domain, define the magnitude or relative magnitude of a problem and target and evaluate interventions. Here, we propose a study of silicosis-related data from mine workers in Rwanda's Eastern Province through the development of a silicosis surveillance and health education program at Rwinkwavu District Hospital.

Study Goal and Objectives

- 1. To assess the prevalence of silicosis among workers in four mines located in the Kayonza District of Rwanda
- 2. To adapt a validated screening tool testing in Dutch construction workers for Rwandan miners

3. To implement an occupational health education program and assess the change of before and after intervention that target towards proper use of PPE and individual risk assessment in mine workers using knowledge-attitudes-practice tool

Methodology:

Study setting:

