The study design will be cross-sectional study and is further detailed in Figure 4. There are three main objectives: silicosis prevalence; baseline silicosis-related knowledge, attitudes and practices (KAP); and the impact of occupational health education. A team of clinical and public health professionals affiliated with Partners In Health/Inshuti Mu Buzima and Rwinkwavu District Hospital will carry out the study with data collection assistance from trained fourth-year medical students from the University of Rwanda during their social medicine rotation. The preparation phase will involve contacting and establishing agreements with stakeholders from key organizations including Rwinkwavu District Hospital, Wolfram Mining and Processing Ltd., University of Rwanda and Partners in Health/Inshuti Mu Buzima. This phase will involve training medical student data collectors and recruiting study subjects. The study execution phase will firstly consist of a cross-sectional analysis of silicosis prevalence, adapting a validated silicosis questionnaire screening tool to the target study population and performing spirometry and chest radiography to all targeted miners [Suarthana, Eva, et al. "A Simple Diagnostic Model for Ruling Out Pneumoconiosis among Construction Workers." Occupational and Environmental Medicine, JSTOR]. This screening tool for ruling out occupational pneumoconioses, and silicosis specifically, was developed by researchers in the Netherlands. We will adapt and validate the use of this screening tool to Rwandan mine workers by comparing the screening results with objective spirometry and chest radiograph findings on all subjects who have spent at least one cumulative year working directly with mining products. Secondly, the execution phase will involve an analysis of existing silicosis-related KAP and the delivery of targeted occupational health education to study subjects followed by a reassessment of knowledge and attitudes. We will perform initial education program and KAP survey at the time of questionnaire based screening with re-assessment at 2-week time point. There are approximately 995 mine workers in the cachement are of this study and our goal is to try and involve all of these stakeholders. Baseline KAP survey will be done prior to our health education program on PPE, environmental

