Participants will be recruited from the mining and processing company Wolfram Mining and Processing Ltd., which operates in Rwinkwavu, Murama, Mwili, and Rurambira sectors. Inclusion criteria for all three study objectives, including silicosis screening, KAP assessment and education programs are: adult residents of Kayonza District aged 18 years or older who regularly (at least once per week) works in direct physical proximity with mining products in operations managed by Wolfram Ltd. at the present time or those who regularly worked in such mining operations for at least one cumulative year within the last 10 years. Exclusion criteria include those who have a significant impairment in speech or hearing due to the limited availability of adequate accessibility provisions for such study subjects, or other physical or medical disability that may limit involvement. Patients who are illiterate may still participate in the study with help from data collectors who can help study candidates complete forms and assessments. Recruitment procedures will be proposed to the managers of Wolfram Ltd. and finalized through consensus. We will propose that those who meet inclusion criteria be informed of the opportunity to receive a free medical screening and important information on staying healthy while working in the mining industry. Mine workers who accept to be a part of study, will avail him/herself two half days. Workers are in the mine in two possible shifts, typical shifts are from 6am-2pm (One site has a night shift from 4pm-early am). We plan to perform screening and education from 2-4pm at each site for workers who agree to participate so that all miners have access to the program. All relevant ethical information, including the risks and benefits of study participation will be provided to each prospective study subject in an informed consent document that will be made available in written and oral form in both Kinyarwanda and English.

Data collection

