Questionnaire data will be collected by trained data collectors and supervised by faculty and other health professionals including Internal Medicine Doctors, and trained healthcare professionals. Data will be collected across two visits, two to four weeks apart. At the first visit, each mine worker and supervisor at mining site will privately undergo a guided oral and structured questionnaire on demographic, socio-economic, and KAP related to silicosis and mining data will be collected. Each participant will be reassured and reminded that individual responses are confidential, inaccessible by the Wolfram Ltd. Company and will be anonymized prior to publication. Mine workers will also undergo an oral and structured questionnaire-based screening for silicosis symptoms. All subjects will then be assembled in small groups to receive targeted health education. At the second visit, mine workers and mining site supervisors will undergo structured interview for retention of health education by fulfilling a repeat KAP questionnaire, identical to the original. Data collected will include percentage of questions answered correctly, and will be further analyzed based on content areas. Mine workers who have worked in mining for at least one cumulative year will also undergo chest radiography and spirometry performed by trained clinical staff at Rwinkwavu District Hospital during their first visit with results interpreted by physician specialists. All questionnaire responses will be documented by data collectors and entered into a computerized database as the questionnaire is being performed. Data will be stored digitally on password-protected hard drives, tablets, and secure cloud servers.

The published sensitivity and specificity of the silicosis screening questionnaire will be reassessed in this study population by comparing the questionnaire results to chest radiography and spirometry findings from each subject.

Pilot Study

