We expect to have a robust understanding of the prevalence of silicosis among Rwandan mine workers along with an understanding of their KAP related to this disease. We expect to see the change of before and after an educational program on silicosis-related KAP. The long-term impact of this study will be to support the institutionalization of a permanent silicosis surveillance and prevention program at Rwinkwavu District Hospital. This will be achieved by first establishing prevalence of silicosis among miners in Kayonza district, and enrollment of miners into a protocolized surveillance program to prevent disease progression and identify/prevent new cases. By further extension, this study is intended to bolster efforts to prevent silicosis through health education and policy change and identify and manage the disease at early stages through universal screening and prompt referral for further medical evaluation and care. Ultimately, impact of surveillance program will be measured by new incidence of silicosis in our study population against average case rates in the general population, as well as retention rates in surveillance protocols.

Dissemination of Results and Publication

We anticipate that the results of the study will be relevant to the larger medical, research, and mining community and will be of particular interest to those clinicians who are practicing in LMICs as well as areas with high prevalence of silicosis and other occupational pneumoconioses. We aim to publish this study in a peer-reviewed journal focused on occupational health, public health, global health or respiratory disease. Lead authors will be those who have contributed most significantly to the successful conceptualization and execution of the project.

Implications for practice, public health and policy

This study will help all stakeholders in mining-related policy formation, decision making, and interventions to eliminate silicosis among miners. These data will inform mining-related occupational health policies in Rwanda and elsewhere. These data will serve as a model for other health facilities and health systems to institutionalize silicosis education and surveillance. The information gleaned and delivered in this study will inform individual health care providers, hospitals and mining company employees and stakeholders regarding the nature of silicosis in Rwanda and mechanisms to prevent, identify, mitigate and ultimately eliminate the disease from this population.

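### Questionnaire accuracy is pooled over all verified workers with no separate result for those without a prior silicosis diagnosis, so sensitivity for undiagnosed disease may be overstated by an unknown amount

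*Combined protocol and SAP*

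**What the plan says.** The Data collection section says that the published sensitivity and specificity of the questionnaire will be reassessed by "comparing the questionnaire results to chest radiography and spirometry findings from each subject". The Study design section narrows who that covers: the comparison uses "objective spirometry and chest radiograph findings on all subjects who have spent at least one cumulative year working directly with mining products". Each subject therefore means each verified subject, not everyone enrolled.

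The recruitment section admits current workers "or those who regularly worked in such mining operations for at least one cumulative year within the last 10 years". Its exclusions are impaired speech or hearing, "or other physical or medical disability that may limit involvement". A previous diagnosis of silicosis is not among them. The section on data management, interpretation and analysis defines no subgroup for the accuracy objective.

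Three other statements bear on the point. The Project Summary reports that "Silicosis among local mine workers is a common reason for hospitalization and death at Rwinkwavu District Hospital", which is the study hospital. The Background says that without regular screening "the diagnosis of silicosis is usually not made until an extensive level of irreversible lung damage", and adds that marked debility is present by then. Under Expected Outcome, the study is meant to help "identify and manage the disease at early stages through universal screening and prompt referral for further medical evaluation and care".

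**The concern.** The questionnaire screens for symptoms, and the Study design section describes the tool it is adapted from as one for ruling out pneumoconiosis. For a rule-out test the costly error is a missed case, and the cases that matter are those nobody has yet recognised. A worker who has already been told the diagnosis does not need the test.

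If such workers are in the accuracy analysis, they probably come from the advanced, symptomatic end of the disease, and they know what they have. They would then screen positive more readily than undiagnosed workers, and the single pooled sensitivity would exceed the sensitivity that applies in future screening. The protocol intends its results to support a permanent surveillance programme and to serve as a model for other facilities, so an inflated figure could be carried into use elsewhere.

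**Working it through.** **No figure to reproduce.** The documents give no expected sensitivity, specificity, sample size or precision for the accuracy objective. The stated sample sizes concern prevalence and the knowledge, attitudes and practices comparison.

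**Formula.** Let f be the share of reference-positive workers who already have a diagnosis, Sk the sensitivity in those workers and Su the sensitivity in undiagnosed cases.

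- Pooled sensitivity = f × Sk + (1 − f) × Su
- Overstatement = pooled − Su = f × (Sk − Su)

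The overstatement is zero if f = 0 or if Sk = Su. Known cases confirmed by the reference tests are all reference-positive, so they do not enter specificity.

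**Size.** All three inputs are assumptions. With Sk = 98% and Su = 75%, the gap is 23 points:

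| f | Pooled sensitivity | Overstatement (points) |
|---|---|---|
| 0% | 75.0% | 0 |
| 5% | 4.9 + 71.25 = 76.15% | 1.15, about 1.2 |
| 10% | 9.8 + 67.5 = 77.3% | 2.3 |
| 20% | 19.6 + 60.0 = 79.6% | 4.6 |
| 30% | 29.4 + 52.5 = 81.9% | 6.9 |

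The result depends on the assumed gap. With Sk = 95% and Su = 70%, the overstatement is 0.10 × 25 = 2.5 points at f = 10% and 0.30 × 25 = 7.5 at f = 30%. With Sk = 95% and Su = 50%, it is 4.5 and 13.5 points.

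**Precision cost of restricting to undiagnosed cases.** Inputs are about 995 workers and 30% prevalence, the low end of the range in the Study sample section, with an assumed Su of 70%. The 95% half-width is 1.96 × √(0.70 × 0.30 / m), where m is the number of cases.

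- All cases: 995 × 0.30 ≈ 298, half-width 5.2 points
- f = 10%: 298.5 × 0.9 ≈ 269 cases, 5.5 points
- f = 30%: 298.5 × 0.7 ≈ 209 cases, 6.2 points

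With the 900 chest films in the budget table instead of 995 workers, the cases are 270, 243 and 189, and the half-widths are 5.5, 5.8 and 6.5 points.

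**The case against.** A reader might infer that workers who know their diagnosis are in the analysis and that sensitivity will be overstated. The documents do not support that. They do not say that any participant has a prior diagnosis, and they give no share. Several features suggest that the share could be small:

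- Diagnosis comes with debility, and the disability exclusion could remove some of those patients.
- Recruitment is through the company, with sessions at the mine sites, which favours people fit enough to work. Former miners are eligible but may be hard to reach this way.
- The Background says that "Rwanda currently lacks an existing body of data on current silicosis prevalence and a surveillance system", so prior diagnosis may be uncommon.
- The statement about hospital admissions and deaths describes the sickest patients, not the workforce of about 995.

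These points stand. They make the bias conditional and extend its range down to zero.

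A reader might also infer that the study does not ask about prior diagnosis. That cannot be established, because the questionnaire is an attachment that is not shown. What can be established is that the described analysis makes no use of such an item. The tool's items and cut-off are not shown either, so the assumed 98% cannot be checked.

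On scale, 900 films at 30–50% prevalence give 270–450 cases and a 95% half-width of about 5.2 to 4.0 points at 75% sensitivity. A 2.3-point shift is about half of that and does not by itself show that a poor tool would look adequate. This is fair, but a larger sample narrows the interval and leaves the bias in place.

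Finally, the stated aim is to reassess accuracy in this study population, which is a reason to keep the all-subject estimate. It is not a reason to report only that estimate when the intended use is early detection.

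**Conclusion.** The concern holds in conditional form. The plan as written yields one pooled sensitivity over all verified workers. It does not separate those with a prior silicosis diagnosis, who are eligible and are likely to exist in the source population. Any who enrol would probably screen positive more often, so upward bias is the likely direction for sensitivity in undiagnosed disease.

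The amount is unknown. With assumed sensitivities of 98% and 75% it runs from 0 to 6.9 points as the share already known goes from 0% to 30%, and a wider assumed gap would raise it. That known cases will in fact be included, and how they will answer, are inferences. The prevalence estimate is not affected. This is an inexpensive improvement to the accuracy objective, not a defect that invalidates it.

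**What to change.** 1. Check whether the attached questionnaire already records a prior diagnosis. If not, add one self-report item asking whether a health worker has ever told the participant that they have silicosis or another dust disease of the lung. Ask it after the symptom screen, so that it does not prime the answers, and before the study's own results are given.
2. State in the analysis section that sensitivity and specificity in verified workers without a prior diagnosis are the estimates that support screening use. Report the all-subject estimates alongside them, with the number of known cases.
3. Keep known cases in the numerator and denominator of the prevalence.

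The cost is at most one questionnaire item, a sentence or two of analysis text, and somewhat fewer cases for sensitivity. In the example of 995 workers, the half-width goes from 5.2 points to about 5.5–6.2. Checking answers against hospital records is optional and not part of this fix; it would need identifiers, staff time and possibly further consent or ethics review.

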Duration

Duration of project, including recruitment, deliver health education, screening, data collection, data analysis, and manuscript preparation, is expected to take 1 year.

Phase one: January 2022 – September 2022: preparation time. Designing study tools, collecting study approvals, contacting stakeholders, and testing study tools.

Phase two: October 2022-January 2023: implementation time. Training, collection, managing, analysis of data, and educating subjects on KAP.

Phase three: February – July 2023: Dissemination phase.

Anticipated Problems

We anticipate potential conflicts of interest between the hospital and the mining company and potentially losing subjects to follow-up. Also, difficulty in obtaining desired clinical data. The study team will do our best to limit anticipated errors

Ethical review and board approval

Approval from IMB Research committee and ethical clearance from RNEC will be requested along with a formal authorizing letter will be presented to Rwinkwavu District Hospital, Partners in Health (PIH) leadership, and local and mining company leaders for obtaining approval. During the recruitment stage, it will be declared to each stakeholder and prospective participant that, beyond the direct benefits of free medical screening and education, no study subject will be compensated or receive any other benefits in return for participation. There will be no penalty for declining to participate and participants may withdraw from the study any time without penalty.

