Participants' privacy and confidentiality will be considered by using both people initials/ IDs for research reason and names for clinical/ treatment purpose. Privacy at health mining site and hospital will be ensured by identifying the private room/ place before starting screening and data collection. This means that the PI will visit screening site and district hospital prior to screening and the data collection for prior place setting and ensure privacy for screening and interviewees. In order to ensure the confidentiality, the study team explained the interviewees that nobody will be shared the information; only study team will share for research purpose. There will be no risks to the participants in this study, this means the study doesn't aim to harm the people and patients but to inform decision makers for preventing silicosis at early stage for risky people/ miners and improving health care. Also, the participants will be informed that there is no compensation/ direct benefit from participating in this study. The benefit of this study is to ensure effective silicosis prevention and improve quality of life for people tested silicosis positive. The researchers will request participants' consent to participate. Those who are able to read will be given consent form and read for themselves and those who weren't able to read researcher or data collector read for them. Researcher/ data collector and people will sign consent form. Data collectors were trained on research ethics prior to data collection and also training will be conducted for allowing them being familiar to study tools and ensure ethic consideration. Data will be both collectors will be fourth year medical students who will collect data during screening and hired qualified study coordinator.

See also attached for both English and Kinyarwanda versions of the consent form and questionnaire.

#	Item	Frequency	Cost	Times/ month	Total
	Research coordinator				
1	salary, half-time	1	400,000	12	4,800,000

Budget: detailed in below table

	Research coordinator		15.000	10	100.000
2	airtime	1	15,000	12	180,000
3	Focal people's airtime	4	12,500	12	600,000
4	Projects updates meeting	1	250,000	4	1,000,000
5	Travel fee	1	30,000	6	180,000
6	Printings	1	25,000	12	300,000
9	CXR-cost	900	6,528	1	5,875,200
10	Dissemination fee	1	4,000,000	1	4,000,000
	Total				

Collaborators

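### The protocol declares that there are no risks and gives participants two incompatible messages about direct benefit; both conflict with its other passages and need one reconciled wording

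*Combined protocol and SAP*

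**What the plan says.** **Risk.** Ethical review and board approval states: "There will be no risks to the participants in this study, this means the study doesn't aim to harm the people". No other reason for the absence of risk is offered there. Under Recruitment of study participants and consent to participate, the protocol commits to the opposite kind of content: "All relevant ethical information, including the risks and benefits of study participation will be provided to each prospective study subject".

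**Procedures.** Under Data collection: "Mine workers who have worked in mining for at least one cumulative year will also undergo chest radiography and spirometry". The budget table carries a line for 900 chest radiographs, and Study sample puts the workforce at around 995.

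**Benefit.** Ethical review and board approval gives two messages. One, to be declared to each stakeholder and prospective participant, is: "beyond the direct benefits of free medical screening and education, no study subject will be compensated or receive any other benefits". The other, further on in the same section, is: "the participants will be informed that there is no compensation/ direct benefit from participating in this study".

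**Employer.** Participants are recruited from one mining company, and the recruitment procedure is to be agreed with its managers. Anticipated Problems states: "We anticipate potential conflicts of interest between the hospital and the mining company".

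**Safeguards.** Data collection promises that individual responses are confidential and closed to the company. It also says that trained clinical staff perform the tests and physician specialists interpret them. The ethics section provides private rooms checked in advance, research identifiers, no penalty for declining, and withdrawal at any time.

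**The concern.** Not intending harm and not exposing anyone to risk are different things, and the protocol offers the first as proof of the second. A protocol that declares no risks also gives the authors of a consent form nothing to put under the risk heading that the recruitment section promises. The benefit conflict is more direct, because both sentences describe what the same people will be told.

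At stake is the accuracy of what the ethics committee approves and of what workers hear before agreeing to a radiograph, a breathing test and the keeping of a diagnosis under their name. No estimate or test in the study depends on it.

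**Working it through.** This is mainly a comparison of text. The one figure involved is checked first.

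**1. The radiograph budget (budget table; Study sample).**
- Cost: 900 × 6,528 × 1 = 5,875,200, which matches the table exactly.
- Share of the workforce: 900 / 995 = 0.9045, or 90.5%.
- Radiographs for all 995 would cost 995 × 6,528 = 6,495,360.
- The 900 is a budgeted count, not an enrolment figure. Radiography is limited to workers with at least one cumulative year in mining, so a number below 995 is not in itself an error. It shows only that radiography is planned for most of the workforce.

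**2. Risk: the passages side by side.**

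| Place | Content |
|---|---|
| Recruitment and consent | Risks will be given to each prospective participant in the consent document |
| Data collection | Radiography and spirometry for workers with at least one cumulative year |
| Ethical review, on privacy | Names are kept for clinical purposes, identifiers for research |
| Institutionalized linkage to care and follow-up | Workers who screen positive are on a different visit schedule from the rest |
| Ethical review, on risk | No risks, because no harm is intended |

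The last row cannot stand beside the first, since a promise to explain risks presupposes that some exist. It also sits badly with the middle rows. Radiography involves exposure to radiation, and a named positive result, followed up on its own schedule, can in principle become known to others. The documents do not label either of these a risk; that step is inferred from the procedures.

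**3. Reach of the safeguards.** The assurance about company access covers questionnaire responses and does not expressly mention radiograph or spirometry results. The no-penalty assurance covers declining and withdrawing, not a positive finding. The safeguards reduce the disclosure risk, but they do not make a statement of no risk true.

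**4. Benefit: the passages side by side.**
- Message A: free screening and education are direct benefits, and there are no others.
- Message B: there is no compensation or direct benefit.
- The recruitment section proposes to invite workers with the offer of a free medical screening, which agrees with A.
- The sentence after message B says that the study should improve quality of life for those who test positive, which also sits poorly with B.

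Message A applies the term direct benefits to the screening and education themselves. Taken at its word, message B denies them.

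**The case against.** The strongest reply is that the sentence on risk is a statement in the protocol and not a message to participants. Only the benefit sentence says that participants will be informed. The protocol says that English and Kinyarwanda consent forms are attached, and they are not in the text reviewed. They may already list the risks correctly. This stands. A reader might infer that workers will be told there are no risks, or that consent would rest on a false statement, but the documents do not support either.

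Other stronger readings also fail:
- **That about 90% of participants receive a false statement.** The 90.5% compares budgeted films with the estimated workforce. It does not count what anyone is told.
- **That the protocol itself foresees employment consequences for workers.** The anticipated conflict of interest is between the hospital and the company, and is listed beside loss to follow-up as an operational problem. It makes careful wording on disclosure reasonable and shows nothing more.
- **That harms go unrecorded because risk was declared nil.** The supplied text has no provision for recording a problem during the tests or a breach of confidentiality, but nothing links that absence to the risk sentence. The objectives are prevalence, adaptation of the screening tool and change in knowledge, attitudes and practices; no conclusion about safety is planned.

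On benefit, the joint wording of compensation and direct benefit may have been meant as payment only. That is a fair reading of the intention, but the other message uses direct benefits for the screening, so the two sentences still have to be reconciled.

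**Conclusion.** The point holds as two wording errors that should be corrected.

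- **Risk.** The no-risk statement rests on a reason that does not support it. It conflicts with the protocol's own promise to explain risks, and with planned radiography, spirometry and the holding of identifiable results. The conclusion assumes only that radiation exposure and disclosure of a result are foreseeable risks of these activities. The documents do not name them as such.
- **Benefit.** The two messages to participants contradict each other within one section. This needs no assumption about the consent form.

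The size is qualitative. Radiography is budgeted for 900 people, so the risk wording concerns a procedure planned for most of the workforce. Sample size, power and analysis do not change.

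**What to change.** 1. In Ethical review and board approval, replace the no-risk sentence with a short statement of the foreseeable risks of the planned procedures and of disclosure of results. Set beside it the safeguards already in Data collection and in the ethics section, and state whether the bar on company access extends to radiograph and spirometry results.
2. Use one benefit sentence wherever benefit is mentioned: free screening and education, with no payment or other benefit.
3. Check the English and Kinyarwanda consent forms against both statements and correct them where they differ.

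Clinical precautions for each procedure are for the investigators to set. Two database fields, one for a problem during either test and one for a reported breach of confidentiality, would be a reasonable addition but are optional.

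The cost is a wording amendment through the ethics committee and, if needed, revised consent forms. The study may look slightly less favourable to prospective participants.
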